6.3 Treatment Period

Subjects receiving metformin and/or doxycycline will return to clinic day 1, week 1. Surgical resection will be scheduled a minimum of 7 days after the start of metformin and/or doxycycline, and a maximum of 5 weeks. The participant will receive a Patient Medication Diary to record the time (AM and PM) and number of pills taken for both Metformin and Doxycycline as applicable based on their randomization.

The following assessments will be performed at Visit 2, the day of surgery

- Physical exam- Pre-operative nursing or anesthesia exam is acceptable and is to be performed the morning of surgery.
- Concomitant medications
- Adverse event assessment
- Patients will undergo their Surgical Resection at Visit 2.
 - When a pre-treatment sample has been acquired by flash freezing for MSI, and if there is excess tissue available at the time of resection, this tissue samples will also be frozen in liquid nitrogen for MSI. A post-treatment tissue sample will be obtained from excess tissue taken from this resection specimen that is not needed in the course of clinical care.
- Correlative studies will be drawn at Visit 2: oncomiR miR-21, serum triglycerides, IGF-1, IGF-BP3, ESR, adiponectin, leptin, IGF-1R, exosome evaluation, metabolomics profile, and microRNA expression profile.
- Study drug will be taken up until at least 12 hours before surgery.

6.4 End of Treatment Study Procedures

The following study activities will occur at End of Study Visit, within 14 days \pm 7 days of stopping the protocol study treatments:

- Concomitant medications
- Adverse event assessment

6.5 Post-treatment/Follow-Up

A follow up phone call will be performed 30 days (\pm 5 days) after the last dose of metformin and doxycycline for any other side effects or adverse events. This is allowed to coincide with the End of Treatment visit if it occurs during timing overlap. The participant's medical records will be reviewed every 3 months for 12 months to assess final pathologic staging.

6.6 Withdrawal Visit/Discontinuation of Therapy

Patients can withdraw at any time during the study if they no longer want to participate in the trial. If withdrawal occurs no further metformin and or doxycycline administration will occur and patients will be required to return remaining tablets which will be logged in to medication administration records and destroyed. If a subject withdraws consent to participate in the study, permission will be sought to use data pertaining to the subject in the analysis as far as they participate and they will be removed from subsequent analyses and replaced.

Description of when a subject's participation in the trial may be discontinued:

Specific reasons for discontinuing a subject from this study are:

1. Voluntary discontinuation by the subject who is at any time free to discontinue their participation in the study, without prejudice to further treatment.
2. Safety reasons as judged by the investigator.
3. Severe non-compliance to the protocol as judged by the investigator.
4. Incorrect enrollment of the subject.
5. Subject lost to follow-up
6. Death

7 Study Procedures and Evaluations

Study procedures for this trial include:

- Review and immunohistochemical staining of a patient's diagnostic biopsy, which was performed as standard of care.
- Randomization to receive metformin alone, doxycycline alone, or metformin and doxycycline together.
- Administration of the oral medication(s) listed above as per randomization until the day before the patient's planned surgery.
- The collection of two serum separator tubes to be drawn after enrollment and prior to the start of the study treatment.
- Meeting with a registered dietitian either in person or by phone to do a guided three day dietary recall log within the first 8 days when possible.
- Snap freezing a portion of the patient's biopsy and resection specimen for MSI testing may be performed in a subgroup of specimens.
- Immunohistochemistry on slides from the patient's resection specimen.

7.1 Study Procedures/Evaluations

- Medical history including intercurrent illnesses and specific attention to diabetes, may be obtained from the medical record
- Physical exam: height, weight, obtained from the medical record

- Concomitant meds: prescription medications taken for the 28 days prior to enrollment
- ECOG performance status from the medical record
- Obtain histologic confirmation of disease from the medical record
- Laboratory tests: Hematology- CBC with differential; Blood Chemistry- Creatinine, AST, AT, ALK Phos T Bili to have been performed within 28 days of enrollment and thus may be obtained either from the medical record or as a part of the standard of care

7.2 Laboratory Procedures/Evaluations

7.2.1 Clinical Laboratory Evaluations

- Hematology: CBC with differential
- Blood Chemistry with Creatinine, AST, AT, ALK Phos T Bili
- Serum or urine pregnancy test

7.2.2 Special Assays or Procedures

Research Correlates- exosome evaluation, microRNA and metabolomics profile.

These labs will be obtained from two serum separator tubes which will be provided directly to the [name] laboratory. After being obtained, the tubes may be kept at room temperature and transported to the laboratory at [name]. Contact [name], MS, Research Associate, [contact].

7.2.3 Specimen Preparation, Handling, and Storage

Biopsy specimens both pre-treatment and post-treatment are to be processed as formalin-fixed paraffin embedded samples per clinical standards.

Samples for MSI testing will be flash frozen in liquid nitrogen within 10 minutes of removal of the specimen by a member of the [name] laboratory. Fresh tissue samples will be quick frozen in liquid nitrogen, transferred to appropriate storage vials and stored at -80C until shipping to Vanderbilt MSI Facility. Each sample storage vial will be labeled with a unique ID number without any PHI.

7.2.4 Specimen Shipment

Flash frozen tumor samples will be shipped to the Mass Spectroscopy Imaging facility at Vanderbilt University on dry ice by the [name] laboratory personnel. For shipping, sample vials are placed into plastic Ziplock bags that are then placed into a styrofoam container of dry ice within a cardboard box. Shipping containers are sent Fed Ex Priority Overnight to the following address:

[name]/[name], Mass Spectrometry Research Center, [name]

8 Evaluation of Safety

8.1 Specification of Safety Parameters

8.1.1 Unanticipated Problems

Unanticipated problems (UAPs) include, in general, any incident, experience, or outcome that meets the following criteria:

- unexpected in terms of nature, severity, or frequency given (a) the research procedures that are described in the protocol-related documents, such as the IRB-approved research protocol and informed consent document; and (b) the characteristics of the subject population being studied;

UAPs are considered to pose risk to subjects or others when they suggest that the research places subjects or others at a greater risk of harm (including physical, psychological, economic, or social harm) than was previously known or recognized.

8.1.2 Adverse Events

An adverse event is any untoward or unfavorable medical occurrence in a human subject, including any abnormal sign (for example, abnormal physical exam or laboratory finding), symptom, or disease, temporally associated with the subject's participation in the research, whether or not considered related to the subject's participation in the research.

8.1.3 Serious Adverse Events

A serious adverse event (SAE) is one that meets one or more of the following criteria:

- Results in death
- Is life-threatening (places the subject at immediate risk of death from the event as it occurred)
- Results in inpatient hospitalization or prolongation of existing hospitalization
- Results in a persistent or significant disability or incapacity
- Results in a congenital anomaly or birth defect
- An important medical event that may not result in death, be life threatening, or require hospitalization may be considered an SAE when, based upon appropriate medical judgment, the event may jeopardize the subject and may require medical or surgical intervention to prevent one of the outcomes listed in this definition.

8.2 Safety Assessment and Follow-Up

The PI will follow adverse events with start dates occurring any time after informed consent is obtained until 7 (for non-serious AEs) or 30 days (for SAEs) after the last day of study participation. At each study visit, the investigator (or designee) will inquire about the occurrence of AE/SAEs since the last visit. Events will be followed for outcome information until resolution or stabilization.

8.3 Recording Adverse Events

The following subsections detail what information must be documented for each adverse event occurring during the time period specified in Section 8.2 Safety Assessment and Follow-Up.

8.3.1 Relationship to Study Intervention

The relationship to study intervention or study participation must be assessed and documented for all adverse events. Evaluation of relatedness must consider etiologies such as natural history of the underlying disease, concurrent illness, concomitant therapy, study-related procedures, accidents, and other external factors.

The following guidelines are used to assess relationship of an event to study intervention:

1. Related (Possible, Probable, Definite)
 - a. The event is known to occur with the study intervention.
 - b. There is a temporal relationship between the intervention and event onset.
 - c. The event abates when the intervention is discontinued.
 - d. The event reappears upon a re-challenge with the intervention.
2. Not Related (Unlikely, Not Related)
 - a. There is no temporal relationship between the intervention and event onset.
 - b. An alternate etiology has been established.

8.3.2 Expectedness

The PI is responsible for determining whether an AE is expected or unexpected. An AE will be considered unexpected if the nature, severity, or frequency of the event is not consistent with the risk information previously described for the intervention. Risk information to assess expectedness can be obtained from preclinical studies, the investigator's brochure, published medical literature, the protocol, or the informed consent document.

8.3.3 Severity of Event

Adverse events will be graded for severity according to the Common Terminology Criteria for Adverse Events (CTCAE) version 4.

8.4 Safety Reporting

8.4.1 Unanticipated Problem Reporting to IRB

All incidents or events that meet criteria for unanticipated problems (UAPs) as defined in Section 8.1.1 Unanticipated Problems require the creation and completion of an unanticipated problem report form (OHR-20).

UAPs that pose risk to subjects or others, and that are not AEs, will be submitted to the IRB on an OHR-20 form via the eazUP system within 5 working days of the investigator becoming aware of the event.

UAPs that do not pose risk to subjects or others will be submitted to the IRB at the next continuing review.

8.4.1 Adverse Event Reporting to IRB

Grade 1 AEs are not required to be reported to the IRB.

Grade 2 AEs will be reported to the IRB at the time of continuing review if, in the opinion of the investigator, they represent events that exceed expected frequency or in some other way are judged to be unexpected and possibly associated with increased risk.

8.4.2 Serious Adverse Event Reporting to IRB

SAEs will be reported to the IRB on OHR-10 forms via the electronic reporting system (eSAEY) according to the required time frames described below.

Grade 3-4 AEs that are unexpected and deemed to be at least possibly or definitely related to the study will be reported to the IRB within 2 working days of knowledge of the event.

Grade 3-4 AEs that are deemed unrelated to the study will be reported to the IRB within 5 working days.

Grade 5 AEs will be reported to the IRB within one working day of knowledge of the event.

8.4.3 Reporting to SKCC DSMC

All AEs and SAEs, safety and toxicity data, and any corrective actions will be submitted to the DSMC per the frequency described in the SKCC DSMP. The report to the SKCC DSMC will also include any unanticipated problems that in the opinion of the PI should be reported to the DSMC.

For expedited reporting requirements, see table below:

DSMC AE/SAE Reporting Requirements

	Grade 1	Grade 2		Grade 3				Grades 4 and 5
	Unexpected and Expected	Unexpected	Expected	Unexpected		Expected		Unexpected and Expected
				With Hospitalization	Without Hospitalization	With Hospitalization	Without Hospitalization	
Unrelated Unlikely	Reviewed at Quarterly DSMC Meeting and IRB Annual Review	Reviewed at Quarterly DSMC Meeting and IRB Annual Review	Reviewed at Quarterly DSMC Meeting and IRB Annual Review	5 Working Days	Reviewed at Quarterly DSMC Meeting and IRB Annual Review	5 Working Days	Reviewed at Quarterly DSMC Meeting and IRB Annual Review	Phase I - 48 Hours (Death: 24 Hours) Phase II - 5 working days
Possible Probably Definite	Reviewed at Quarterly DSMC Meeting and IRB Annual Review	Reviewed at Quarterly DSMC Meeting and IRB Annual Review	Reviewed at Quarterly DSMC Meeting and IRB Annual Review	48 Hours (Death: 24 Hours)	Phase I - 48 Hours	48 Hours (Death: 24 Hours)	Reviewed at Quarterly DSMC Meeting and IRB Annual Review	Phase I and Phase II - 48 Hours (Death: 24 Hours)

8.4.4 Reporting of Pregnancy

Pregnant women are excluded from this trial. Should a woman of child-bearing potential become pregnant during the course of this trial she will be discontinued from treatment and replaced in the study.

8.5 Halting Rules

This study will be monitored by the SKCC DSMC.

Acute toxicity will be monitored using CTCAE version 4.0 criteria during therapy and up to 30-days post completion of surgical resection. If the lowest dose of metformin and doxycycline develop toxicity ≥ 4 , the study may be terminated after discussion with PI and sponsor.

9 Study Oversight

In addition to the PI's responsibility for oversight, study oversight will be under the direction of the SKCC's Data and Safety Monitoring Committee (DSMC). The DSMC operates in

compliance with a Data and Safety Monitoring Plan (DSMP) that is approved by the Clinical Trials Oversight Committee (CTOC).

10 Clinical Site Monitoring and Auditing

Clinical site monitoring and auditing is conducted to ensure that the rights of human subjects are protected, that the study is implemented in accordance with the protocol and/or other operating procedures, and that the quality and integrity of study data and data collection methods are maintained. Monitoring and auditing for this study will be performed in accordance with the SKCC's Data and Safety Monitoring Plan (DSMP) developed by the SKCC Data and Safety Monitoring Committee (DSMC). The DSMP specifies the frequency of monitoring, monitoring procedures, the level of clinical site monitoring activities (e.g., the percentage of subject data to be reviewed), and the distribution of monitoring reports. Some monitoring activities may be performed remotely, while others will take place at the study site(s). Appropriate staff will conduct monitoring activities and provide reports of the findings and associated action items in accordance with the details described in the DSMP.

11 Statistical Considerations

11.1 Study Hypotheses

Primary: Exposure to metformin and/or doxycycline administered together will alter the metabolic profile of squamous cell carcinoma of the head and neck, specifically as measured by the expression level of CAV1 in tumor-associated stromal cells.

Secondary: Exposure to metformin and/or doxycycline administered together will alter the metabolic profile of squamous cell carcinoma of the head and neck, as measured by the expression levels of BGAL and MCT4 in tumor associated stroma, and TUNEL, MCT1 and TOMM20 in epithelial tumor cells. We hypothesize that these drugs, given either as monotherapy or in combination will be safe and tolerable for patients in the pre-surgical period.

11.2 Analysis Plans

Analysis for primary outcomes: The primary objective of the study is to assess the impact of metformin and or doxycycline on CAV1 expression by immunohistochemistry (IHC) in tumor-associated stromal cells. All patients from whom samples are obtained both pre- and post-treatment will be included in the primary analyses. Within-patient change in IHC scores will be analyzed using the Wilcoxon signed-rank test. Comparisons will be made between pre-treatment and post-treatment within each of the cohorts. The study is not powered to make comparisons between the three different cohort groups.

Analysis for secondary outcomes: Analysis of change in TUNEL, BGAL, TOMM20, MCT1, and MCT4 will be performed using the Wilcoxon signed-rank test. Safety will be provided in descriptive tables.

11.2.1 Safety Review

Incidence of DLTs will be monitored continuously with potential stopping after 10 patients have been enrolled based on the Bayesian method of Thall and Simon. We are comparing our experimental treatment to a standard of no treatment and assume no DLTs under standard of care. Both agents are extremely safe and DLTs should be exceedingly rare. In 900 patients treated with metformin alone, the discontinuation rate was 0.6%. In 31 patients treated with IV doxycycline, 4 SAEs were observed, but none were related to the study drug. Thus, it is reasonable to assume a prior distribution for the DLT rate in the combination of Beta (0.04,1.96). That is, we assume a 2% event rate for the combination with information equivalent to data from 2 patients. We will stop the study for safety if the posterior probability that the rate of DLTs in the combination treatment is 5% or greater is greater than 90%. Stopping rules are outlined in the table below.

Number of patients enrolled	Stop if number of patients with Grade 3 or higher toxicities is \geq
10	2
11-22	3
23-35	4
36	5

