3.2 Number of Subjects

33 total, 11 in each arm

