11.3.2 Accrual Estimates

Our total goal is 33 patients. We estimate this will be possible in a 3-year period with 11 per year.

12 Source Documents and Access to Source Data/Documents

Study staff will maintain appropriate medical and research records for this study, in compliance with ICH E6, and regulatory and institutional requirements for the protection of confidentiality of subject information. Study staff will permit authorized representatives of SKCC and regulatory agencies to examine (and when required by applicable law, to copy) research records for the purposes of quality assurance reviews, audits, and evaluation of the study safety, progress and data validity.

13 Quality Control and Quality Assurance

The investigator will allocate adequate time for monitoring activities. The Investigator will also ensure that the medical monitor or other compliance or quality assurance reviewer is given access to all of the above noted study-related documents and study related facilities (e.g. pharmacy, diagnostic laboratory, etc.), and has adequate space to conduct the monitoring visit.

14 Ethics/Protection of Human Subjects

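### The safety rule has no numeric limit before 10 patients, although two DLTs already meet the plan's own stopping criterion at every count from 2 to 10

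*Combined protocol and SAP*

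**What the plan says.** Section 11.2.1 (Safety Review) gives the rule in full.

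- Prior: "it is reasonable to assume a prior distribution for the DLT rate in the combination of Beta (0.04,1.96"), explained as "we assume a 2% event rate for the combination with information equivalent to data from 2 patients".
- Criterion, with a cutoff of 90%: "We will stop the study for safety if the posterior probability that the rate of DLTs in the combination treatment is 5% or greater is" above that cutoff.
- Timing: "Incidence of DLTs will be monitored continuously with potential stopping after 10 patients have been enrolled based on the Bayesian method of Thall and Simon".
- Table: the second column is headed "Stop if number of patients with Grade 3 or higher toxicities is" at or above the number shown. The limits are 2 at n=10, 3 at n=11-22, 4 at n=23-35 and 5 at n=36. There is no row below 10, and no reason is given for that starting point.

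Section 3.2 plans "33 total, 11 in each arm". On accrual, section 11.3.2 says "We estimate this will be possible in a 3-year period with 11 per year".

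Other provisions can act at any enrolment count. Section 2.2.2 requires immediate notification of grade 3 or 4 SAEs. Section 4.5 allows termination for unacceptable risk. Section 8.4.3 sets expedited reporting to the DSMC. Section 8.5 allows termination, after discussion, for toxicity of grade 4 or above at the lowest dose.

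**The concern.** The criterion is a statement about a posterior probability, and that probability can be computed after any number of patients. If two DLTs occur among the first few patients, the stated 90% cutoff is passed, but the table offers no limit to compare them with until the tenth patient is enrolled. A minimum sample normally earns its place by protecting against a stop on thin data that later patients would have reversed. Here it is not clear that any such reversal is possible. If it is not, the minimum buys nothing, and patients enrolled between the second DLT and the tenth patient are exposed after the outcome of the rule is settled. That would happen in the period when least is known about giving the two drugs together.

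**Working it through.** **Inputs.** Prior Beta(0.04, 1.96), threshold rate 0.05, cutoff 0.90 and the table limits are from 11.2.1. Planned size of 33 is from 3.2. True DLT rates of 2% to 30% are assumptions that span the plan's 2% expectation, its 5% threshold and higher rates. Patients are treated as independent with a common rate, events are counted promptly, and DLT is equated with the table's grade 3 or higher toxicity.

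**Formula.** After x events in n patients, the posterior is Beta(0.04 + x, 1.96 + n − x). Stop if Pr(rate ≥ 0.05) = 1 − F(0.05; 0.04 + x, 1.96 + n − x) exceeds 0.90, where F is the beta distribution function.

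**Step 1: reproduce the printed table.** Each printed limit is the smallest x that passes the cutoff:

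| n | one event below the limit | at the limit |
|---|---|---|
| 10 | x=1: 0.589 | x=2: 0.905 |
| 11 | x=2: 0.889 | x=3: 0.982 |
| 23 | x=3: 0.890 | x=4: 0.972 |
| 36 | x=4: 0.893 | x=5: 0.966 |

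At the upper ends of the ranges, 3 of 22 gives 0.90005 and 4 of 35 gives 0.9006, both just above 0.90. The table reproduces throughout, so the model used below is the plan's own.

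**Step 2: apply the same formula below n=10.**

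| n | 2 | 3 | 4 | 5 | 6 | 7 | 8 | 9 | 10 |
|---|---|---|---|---|---|---|---|---|---|
| x=2 | 0.994 | 0.988 | 0.980 | 0.970 | 0.959 | 0.947 | 0.934 | 0.920 | 0.905 |
| x=1 | 0.871 | 0.830 | 0.791 | 0.753 | 0.717 | 0.683 | 0.650 | 0.619 | 0.589 |

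Two events pass at every n from 2 to 10; one event passes at none of them. The exception is n=1, where one event in one patient gives 0.914. The implied limit for n=2-10 is therefore 2, the same as the printed n=10 row.

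**Step 3: does waiting prevent any stop?** If x ≥ 2 at some n below 10, then x ≥ 2 at n=10, where the table stops. Conversely, any trial stopped at n=10 has x ≥ 2. The two schemes therefore stop the same trials by n=10 and are identical afterwards.

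**Step 4: size.** An exact recursion was run over 33 patients: the event-count distribution is updated one patient at a time and the probability at or above the limit is removed. It was run with the limit of 2 starting at n=10 and at n=2.

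| True rate | Pr(2 or more events in first 9) | Pr(stop), either start | Expected enrolment, from 10 | from 2 | Saved |
|---|---|---|---|---|---|
| 2% | 1.3% | 2.3% | 32.55 | 32.51 | 0.04 |
| 5% | 7.1% | 15.8% | 30.24 | 29.99 | 0.25 |
| 10% | 22.5% | 52.7% | 24.09 | 23.24 | 0.85 |
| 20% | 56.4% | 94.1% | 14.5 | 12.1 | 2.4 |
| 30% | 80.4% | 99.7% | 11.1 | 7.2 | 3.9 |

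When the second event does fall within the first nine patients, the mean number enrolled before the table can act is 3.4 at a 2% rate, rising to 4.9 at 30%. The maximum is 8 (second event in patient 2).

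**Step 5: how long the rule is silent.** If n counts all patients, 10 patients at 11 per year take 10/11 × 12 = 10.9 months. If n counts only the combination arm, the first limit falls at the tenth of 11 patients. The document does not settle which applies.

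**The case against.** The 10-patient minimum is declared in the same sentence as continuous monitoring, and the table follows it. A minimum before monitoring is a common design choice. A reader might infer that text and table contradict each other; they do not. The point is that the minimum does no useful work against a two-event stop.

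A reader might also infer that nothing can halt the study before the tenth patient. The document does not support that. Sections 4.5 and 8.5 allow termination at any count, sections 2.2.2 and 8.4.3 bring serious events to the oversight bodies quickly, and section 5.4 governs interruption in individual patients. What stands is narrower: these provisions are discretionary or concern reporting, and none sets a number of DLTs at which the study stops.

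The saving is small where the plan expects to be. At true rates of 2% and 5% it is well under one patient, and 11.2.1 regards DLTs as very rare. This limits the practical weight of the point. However, the rule exists for the case in which that expectation is wrong, and the prior behind it is worth only two patients.

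Finally, the minimum does have one real function. With no minimum at all, one DLT in the first patient would meet the criterion (0.914). That justifies a minimum of 2, not of 10.

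**Conclusion.** The point holds for the formal Bayesian rule. Two DLTs meet the stated criterion from the second patient on, the table cannot respond before the tenth, and the delay changes only when the study stops, never whether it stops. The cost ranges from 0.04 patients in expectation at a true 2% rate to 3.9 at 30%. It is a worthwhile improvement, not an error that invalidates the rule.

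The equality of stopping probabilities rests on prompt counting of events and was shown for the printed table over 33 patients. Two definitions need settling alongside it: whether n counts all patients or only the combination arm (the criterion names the combination, but the table runs to 36), and what a DLT is, since the text says DLT while the table counts grade 3 or higher toxicity.

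A related but separate weakness is that the printed limit of 2 applies at a single enrolment count, because 2 of 11 gives 0.889 and the limit rises to 3. At 11 patients per year that row is current for about 365/11 = 33 days, while dosing can last up to 35 days and toxicity is followed to 30 days after surgery (section 8.5). A second event in the ninth or tenth patient could thus be reported after the limit has moved. It would go too far to conclude that n must be redefined as assessed patients with no effect on false stops: the equality above was not shown for that change.

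**What to change.** In the 11.2.1 table, replace the first row (10: 2) with 2-10: 2. In the text, replace the 10-patient minimum with a minimum of 2 patients, so that one DLT in one patient does not stop the study and text and table still agree. Both changes follow from the plan's existing prior, threshold and cutoff; no new criterion is introduced. The cost is one table row and one clause, and the false-stop probability does not change under prompt counting.

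In the same amendment, state which patients n counts and define the event. Separately, the sponsor should consider whether n should count patients who have been assessed instead of patients enrolled, and should compute the operating characteristics of that version before adopting it.
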